## 6.6. Exploratory Analyses

The below exploratory analyses of immunogenicity may be performed:

- GMT and GMFR (compared to Day 1) to vaccine mismatched strains
- GMT and GMFR (compared to Day 1) to vaccine matched and mismatched strains assayed by alternative methods (eg, microneutralization assay for influenza or ligand-binding assay for SARS-CoV-2)
- Frequency, magnitude, and phenotype of virus-specific T-cell and B-cell responses measured by flow cytometry or other methods, and to perform targeted repertoire analysis of B cells and T cells after vaccination
- Frequency, specificities, or other endpoints to be determined for the further characterization of immune responses
- Frequency of laboratory-confirmed clinical influenza and COVID-19 and assessment of immune responses to infection and viral isolates

## 6.7. Planned Analyses

One IA and final analysis will be conducted in the study.

### 6.7.1. Interim Analyses

An IA will be performed on the data from 550 participants, after they have completed Day 29 visit, and will include the safety and immunogenicity data collected up to Day 29. Either nAb or bAb assay will be used for assessment of immunogenicity on all participants. The IA will be performed by a separate team of unblinded programmers and statisticians. The analysis will be presented by vaccination groups. Except for a limited number of Sponsor and CRO personnel who will be unblinded to perform the IA, the study site staff, investigators, study monitors, and participants will remain blinded until after the final database lock for final analysis (mRNA-1073-P101 Data Blinding Plan).

### 6.7.2. Final Analyses

The final analysis of all endpoints will be performed after all participants completed Day 181/EoS. Results of this analysis will be presented in a final CSR, including individual listings. The final CSR will include full analyses of all safety and immunogenicity data through Day 181/EoS. For immunogenicity analysis, either nAb or bAb assays will be used in the study.

## 7. Changes from Planned Analysis in Protocol

There are no changes in planned analysis.

## 9. Appendices

### 9.1.1. Appendix A Standards for Safety and Immunogenicity Variable Display in TFLs

**Continuous Variables:** The precision for continuous variables will be based on the precision of the data itself. The mean and median will be presented to one decimal place

more than the original results; the SD will be presented to two decimal places more than the original results; the minimum and maximum will be presented to the same precision as the original results.

**Categorical Variables:** Percentages will be presented to 1 decimal place.

### 9.1.2. Appendix A Analysis Visit Windows

Analysis visit windows will be utilized for immunogenicity assessments only.

Data will be mapped using the following approach:

Step 1: If the assessments are collected at a scheduled visit, the collected data will be mapped to the nominal scheduled visit.

Step 2: If the assessments are collected at an unscheduled visit, the collected data will be mapped using the analysis visit windows described in Table 6 below.

If a subject has multiple assessments within the same analysis visit, the following rule will be used:

- If multiple assessments occur within a given analysis visit, the assessment closest to the target study day will be used.
- If there are 2 or more assessments equal distance to the target study day, the last assessment will be used.

**Table 6: Analysis Visit Windows for Immunogenicity Assessments**

Visit	Visit Window in Study Day
Day 1	1, Pre-vaccination
Day 8	[2, 18]
Day 29	[19, 105]
Day 181	$\geq 106$

### 9.1.3. Appendix C Imputation Rules for Missing Prior/Concomitant Medications and Non-Study Vaccinations

Imputation rules for missing or partial medication start/stop dates are defined below:

1. Missing or partial medication start date:

- If only Day is missing, use the first day of the month, unless:
  - The medication end date is after the date of injection or is missing AND the start month and year of the medication coincide with the start month and year of the injection. In this case, use the date of the injection
- If Day and Month are both missing, use the first day of the year, unless:
  - The medication end date is after date of the injection or is missing AND the start year of the medication coincide with the start year of the injection. In this case, use the date of the injection
- If Day, Month and Year are all missing, the date will not be imputed, but the medication will be treated as though it began prior to the injection for purposes of determining if status as prior or concomitant.

2. Missing or partial medication stop date:

- If only Day is missing, use the earliest date of (last day of the month, study completion, discontinuation from the study, or death).
- If Day and Month are both missing, use the earliest date of (last day of the year, study completion, discontinuation from the study, or death).
- If Day, Month and Year are all missing, the date will not be imputed, but the medication will be flagged as a continuing medication.

In summary, the prior, concomitant or post categorization of a medication is described in [Table 5](#) below.

**Table 5 Prior, Concomitant, and Post Categorization of a Medication**

Medication Start Date	Medication Stop Date		
	< Injection Date	≥ Injection Date and ≤ Injection Date + 27 days	> 27 Days After Injection [2]
< Injection Date [1]	P	PC	PCA
≥ Injection date and ≤ 27 days after injection	-	C	CA
> 27 days after injection	-	-	A

A: Post; C: Concomitant; P: Prior

[1] includes medications with completely missing start date

[2] includes medications with completely missing end date

#### 9.1.4. Appendix D Imputation Rules for Missing AE dates

Imputation rules for missing or partial AE start dates and stop dates are defined below:

1. Missing or partial AE start date:

- If only DAY is missing, use the first day of the month, unless:
  - The AE end date is after the date of injection or is missing AND the start month and year of the AE coincide with the start month and year of the injection. In this case, use the date and time of injection, even if time is collected.
- If DAY and Month are both missing, use the first day of the year, unless:
  - The AE end date is after the date of injection or is missing AND the start year of the AE coincides with the start year of the injection. In this case, use the date of injection
- If DAY, Month and Year are all missing, the date will not be imputed. However, if the AE end date is prior to the date of injection, then the AE will be considered a pre-treatment AE. Otherwise, the AE will be considered treatment-emergent.

2. Missing or partial AE end dates will not be imputed.

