- 7 days following vaccination: this period includes the day of vaccination and 6 subsequent days, or up to the study discontinuation or death, whichever comes earlier. This analysis period will be used for solicited local and systemic AR that occur during this time.
- Up to 28 days following vaccination: starts from the day of vaccination (Day 1) and spans 28 days to include the day of vaccination and 27 subsequent days, or up to the study discontinuation or death, whichever comes earlier. This analysis period

will be used as the primary analysis period for safety analyses including unsolicited AE, except for solicited AR, unless specified otherwise.

**Study day relative to the injection** will be calculated as below:

- a) study day prior to the injection will be calculated as: date of assessment/event – date of the injection;
- b) study day on or after the date of the injection will be calculated as: date of assessment/event – date of the injection + 1;

**For calculation regarding antibody levels/titers**, antibody values reported as below the lower limit of quantification (LLOQ) will be replaced by  $0.5 \times \text{LLOQ}$ . Values that are greater than the upper limit of quantification (ULOQ) will be converted to the ULOQ if actual values are not available. Missing results will not be imputed.

**Unscheduled visits:** Unscheduled visit measurements will be included in the analyses as follows:

- In scheduled visit windows per specified visit windowing rules.
- In the derivation of baseline/last on-treatment measurements.
- In the derivation of maximum/minimum on-treatment values and maximum/minimum change from baseline values for safety analyses.
- In individual subject data listings.

**Visit window rules:** The analysis visit windows for protocol-defined visits are provided in [Appendix B](#).

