#### **6.4.2. Unsolicited Treatment-emergent Adverse Events**

A treatment-emergent AE (TEAE) is defined as any event occurring during the study not present before exposure to the IP or any event already present that worsens after exposure to IP. Worsening of a pre-existing condition after vaccination will be reported as a new AE.

Adverse events will also be evaluated by the investigator for the coexistence of MAAE which is defined as an AE that leads to an unscheduled visit to a healthcare practitioner.

Unsolicited AEs will be coded by PT and SOC using MedDRA and summarized by vaccination group.

Unsolicited AEs will be collected for up to 28 days after IP dose; SAEs, MAAEs, AESIs, and AEs leading to withdrawal will be collected throughout the study. Analyses of unsolicited AE will be provided for up to 28 days after vaccination unless otherwise specified. SAE, AESI, MAAE, and AE leading to discontinuation from the study up to 28 days after vaccination and throughout the study (up to Day 181/End of Study) will be summarized. Up to 28 days after vaccination period will be used as the primary analysis period for Unsolicited AEs.

All summary tables (except for the overall summary of AEs) for unsolicited AEs will be presented by SOC and PT or by PT only for TEAEs with counts of participants included. SOC will be displayed in internationally agreed order. PTs will be displayed in descending order of frequency in the mRNA-1073 CCI group and then alphabetically within SOC. When summarizing the number and percentage of participants with an event, participants with multiple occurrences of the same AE or a continuing AE will be counted once. Only the maximum severity level will be presented in the severity summaries, and the strongest relationship level will be presented in the relationship summaries.

Percentages will be based upon the number of participants in the Safety Set within each treatment group.

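### Appendix D classes an AE that ended on the injection day as pre-treatment when its start date is partly known, but as treatment-emergent when the start date is wholly missing

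*SAP*

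**What the plan says.** SAP Appendix D (Section 9.1.4) has three branches for a missing AE start date.

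- **Day missing.** The default is the first of the month: "If only DAY is missing, use the first day of the month, unless" an exception applies. The exception, which substitutes the injection date, reads "The AE end date is after the date of injection or is missing AND the start month and year of the AE coincide" with those of the injection.
- **Day and month missing.** The default is the first of the year. The exception has the same form: "The AE end date is after the date of injection or is missing AND the start year of the AE coincides" with that of the injection.
- **Everything missing.** "If DAY, Month and Year are all missing, the date will not be imputed". Status then rests on the end date alone: "if the AE end date is prior to the date of injection, then the AE will be considered a pre-treatment AE". In all other cases the AE is treatment-emergent.

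Section 6.4.2 defines a TEAE as an event that was not present before exposure, or one that worsened after it. Section 6.1 puts the injection day inside the post-injection period: the 28-day window "starts from the day of vaccination (Day 1) and spans 28 days to include the day of vaccination and 27 subsequent days".

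**The concern.** The first two branches require the end date to be strictly later than injection before they give the AE the benefit of the doubt. The third requires it to be strictly earlier before it withholds that benefit. An end date equal to the injection date falls between the two tests, so the outcome depends on how much of the start date happens to be recorded. The better-documented record gets the less conservative status.

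An AE that starts and resolves within hours of the injection, recorded with an incomplete onset date, is a plausible acute reaction to the vaccine. If it is classed as pre-treatment, it leaves the 28-day tables and also the whole-study TEAE tables in Sections 6.4.2.1 and 6.4.2.2. The frequency and severity of unsolicited AEs over 28 days is a primary endpoint (Section 3.1).

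**Working it through.** The plan states no figure on this point, so the check applies the three branches as written.

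**Inputs.** The Appendix D rules above, and the study-day rule in Section 6.1: before injection, day = event date − injection date; on or after injection, day = event date − injection date + 1. The injection date of 15 June 2022 is an example chosen for illustration. Each cell gives the imputed start, its study day and the resulting status.

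| AE end date | Start known as June 2022 | Start known as 2022 | Start wholly missing |
|---|---|---|---|
| 14 June | 1 June, Day −14, pre-treatment | 1 January, Day −165, pre-treatment | no date, pre-treatment |
| **15 June** | **1 June, Day −14, pre-treatment** | **1 January, Day −165, pre-treatment** | **no date, treatment-emergent** |
| 16 June | 15 June, Day 1, treatment-emergent | 15 June, Day 1, treatment-emergent | no date, treatment-emergent |
| Missing | 15 June, Day 1, treatment-emergent | 15 June, Day 1, treatment-emergent | no date, treatment-emergent |

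Study days: 1 June − 15 June = −14. From 1 January to 15 June is 31 + 28 + 31 + 30 + 31 + 14 = 165 days, hence −165.

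The branches agree in every row except the one where the end date equals the injection date.

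**How general this is.** For a same-day end date, the default start equals the injection date only if injection fell on the first of a month (12 dates a year) or on 1 January (1 date). The status therefore differs from the wholly-missing branch on 365 − 12 = 353 injection dates with the day missing, and on 365 − 1 = 364 with day and month missing.

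**After the change.** With *on or after* in both exceptions, the 15 June row becomes 15 June, Day 1, treatment-emergent in the first two columns and matches the third. The other rows do not change.

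**Size per record.** One participant is 1/100 = 1 percentage point in an arm of 100 and 1/50 = 2 points in the arm of 50. The percentage with any TEAE moves only if the lost event was that participant's only TEAE, since Section 6.4.2 counts each participant once for repeated occurrences.

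**The case against.** The strongest reply is that the branches never apply to the same record. An AE has one pattern of missing date, so the program is fully determined and no record receives two statuses. That stands: this is an inconsistent boundary, not two conflicting instructions for one event.

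The strict condition can also be defended. An event that was over by the vaccination day, with onset known only to the month or year, may well have begun earlier. Appendix C uses the same strict wording for medications, so it may be a house convention. The first argument is fair, but it applies just as well to a wholly undated event, which Appendix D treats the other way. The second carries less weight: the medication table in Appendix C also uses the stop date and counts a drug stopped on the injection day as concomitant. There the strict wording does not remove the record; for AEs it does.

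Two stronger readings are tempting, and the SAP does not support them.

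- A reader might infer that a wholly undated TEAE drops out of the 28-day tables because it has no study day. The SAP never says so. It classes the event as treatment-emergent, and for ordinary events "Unsolicited AEs will be collected for up to 28 days after IP dose", so one of these can reasonably be placed in the window. The end-of-study overview takes all reported events in any case. The open question concerns mainly SAEs, MAAEs, AESIs and AEs leading to withdrawal, which are collected throughout.
- A reader might infer that Appendix D can only remove events. It does not: the partial-date exceptions move ongoing or later-ending events onto Day 1, and the wholly-missing rule includes everything that did not end before injection.

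**Conclusion.** The point holds in a narrow form. For an AE ending on the injection day, Appendix D gives pre-treatment status if the month or year of onset is known and coincides with that of injection, and treatment-emergent status if nothing is known. The first outcome removes a possible Day 1 event from all TEAE tables. The SAP's own convention, with the injection day as Day 1 of the post-injection period, favours the second.

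The weight is minor. It takes an incomplete start date together with a same-day end date. The SAP gives no frequency for such records, and they are assumed to be rare. All analyses are descriptive, and unsolicited AEs are reported as counts and percentages, so no test or planned interval is affected. The conclusion assumes that an imputed start before injection makes the AE pre-treatment. That follows from the TEAE definition, unless the event is recorded as a worsening.

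**What to change.** In both partial-date exceptions of Appendix D, replace *after* the date of injection by *on or after* the date of injection. This aligns them with the wholly-missing rule and with the Day 1 convention in Section 6.1.

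The cost is two extra words in each of two bullets and a one-operator change in the program, best made before unblinding. The downside is that an occasional event which began before vaccination and resolved that day would be counted as treatment-emergent. For safety, that is the conservative direction.

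Optionally, add a sentence saying how a wholly undated TEAE is assigned to the 28-day period. This is a clarification, not a correction. A blanket rule that gives all such events the injection date would also bring SAEs, MAAEs and AESIs with much later end dates into the 28-day tables, so the sentence should address events collected throughout the study.

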#### 9.1.5. Appendix E Severity Grading of Laboratory Abnormalities

Serum*	Mild (Grade 1)	Moderate (Grade 2)	Severe (Grade 3)	Potentially Life Threatening (Grade 4)**

Sodium – Hyponatremia mEq/L	132 – 134	130 – 131	125 – 129	< 125
Sodium – Hypernatremia mEq/L	144 – 145	146 – 147	148 – 150	> 150
Potassium – Hyperkalemia mEq/L	5.1 – 5.2	5.3 – 5.4	5.5 – 5.6	> 5.6
Potassium – Hypokalemia mEq/L	3.5 – 3.6	3.3 – 3.4	3.1 – 3.2	< 3.1
Glucose – Hypoglycemia mg/dL	65 – 69	55 – 64	45 – 54	< 45
Glucose – Hyperglycemia Fasting – mg/dL Random – mg/dL	100 – 110 110 – 125	111 – 125 126 – 200	>125 >200	Insulin requirements or hyperosmolar coma
Blood Urea Nitrogen (BUN) mg/dL	23 – 26	27 – 31	> 31	Requires dialysis
Creatinine – mg/dL	1.5 – 1.7	1.8 – 2.0	2.1 – 2.5	> 2.5 or requires dialysis
Calcium – hypocalcemia mg/dL	8.0 – 8.4	7.5 – 7.9	7.0 – 7.4	< 7.0
Calcium – hypercalcemia mg/dL	10.5 – 11.0	11.1 – 11.5	11.6 – 12.0	> 12.0
Magnesium – hypomagnesemia mg/dL	1.3 – 1.5	1.1 – 1.2	0.9 – 1.0	< 0.9
Phosphorous – hypophosphatemia mg/dL	2.3 – 2.5	2.0 – 2.2	1.6 – 1.9	< 1.6
CPK – mg/dL	1.25 – 1.5 x ULN***	1.6 – 3.0 x ULN	3.1 – 10 x ULN	> 10 x ULN
Albumin – Hypoalbuminemia g/dL	2.8 – 3.1	2.5 – 2.7	< 2.5	--
Total Protein – Hipoproteinemia g/dL	5.5 – 6.0	5.0 – 5.4	< 5.0	--
Alkaline phosphate – increase by factor	1.1 – 2.0 x ULN	2.1 – 3.0 x ULN	3.1 – 10 x ULN	> 10 x ULN
Liver Function Tests –ALT, AST increase by factor	1.1 – 2.5 x ULN	2.6 – 5.0 x ULN	5.1 – 10 x ULN	> 10 x ULN
Bilirubin – when accompanied by any increase in Liver Function Test increase by factor	1.1 – 1.25 x ULN	1.26 – 1.5 x ULN	1.51 – 1.75 x ULN	> 1.75 x ULN
Bilirubin – when Liver Function Test is normal; increase by factor	1.1 – 1.5 x ULN	1.6 – 2.0 x ULN	2.0 – 3.0 x ULN	> 3.0 x ULN
Cholesterol	201 – 210	211 – 225	> 226	---
Pancreatic enzymes – amylase, lipase	1.1 – 1.5 x ULN	1.6 – 2.0 x ULN	2.1 – 5.0 x ULN	> 5.0 x ULN

\* The laboratory values provided in the tables serve as guidelines and are dependent upon institutional normal parameters. Institutional normal reference ranges should be provided to demonstrate that they are appropriate.

\*\* The clinical signs or symptoms associated with laboratory abnormalities might result in characterization of the laboratory abnormalities as Potentially Life Threatening (Grade 4). For example, a low sodium value that falls within a Grade 3 parameter (125-129 mEq/L) should be recorded as a Grade 4 hyponatremia event if the participant had a new seizure associated with the low sodium value.

\*\*\*ULN” is the upper limit of the normal range.

Hematology *	Mild (Grade 1)	Moderate (Grade 2)	Severe (Grade 3)	Potentially Life Threatening (Grade 4)
Hemoglobin (Female) - mg/dL	11.0 – 12.0	9.5 – 10.9	8.0 – 9.4	< 8.0
Hemoglobin (Female) change from baseline value - mg/dL	Any decrease – 1.5	1.6 – 2.0	2.1 – 5.0	> 5.0
Hemoglobin (Male) - mg/dL	12.5 – 13.5	10.5 – 12.4	8.5 – 10.4	< 8.5
Hemoglobin (Male) change from baseline value – mg/dL	Any decrease – 1.5	1.6 – 2.0	2.1 – 5.0	> 5.0
WBC Increase - cell/mm 	10,800 – 15,000	15,001 – 20,000	20,001 – 25,000	> 25,000
WBC Decrease - cell/mm 	2,500 – 3,500	1,500 – 2,499	1,000 – 1,499	< 1,000
Lymphocytes Decrease - cell/mm 	750 – 1,000	500 – 749	250 – 499	< 250
Neutrophils Decrease - cell/mm 	1,500 – 2,000	1,000 – 1,499	500 – 999	< 500
Eosinophils - cell/mm 	650 – 1500	1501 - 5000	> 5000	Hypereosinophilic
Platelets Decreased - cell/mm 	125,000 – 140,000	100,000 – 124,000	25,000 – 99,000	< 25,000
PT – increase by factor (prothrombin time)	1.0 – 1.10 x ULN**	1.11 – 1.20 x ULN	1.21 – 1.25 x ULN	> 1.25 ULN
PTT – increase by factor (partial thromboplastin time)	1.0 – 1.2 x ULN	1.21 – 1.4 x ULN	1.41 – 1.5 x ULN	> 1.5 x ULN
Fibrinogen increase - mg/dL	400 – 500	501 – 600	> 600	--
Fibrinogen decrease - mg/dL	150 – 200	125 – 149	100 – 124	< 100 or associated with gross bleeding or disseminated intravascular coagulation (DIC)

\* The laboratory values provided in the tables serve as guidelines and are dependent upon institutional normal parameters. Institutional normal reference ranges should be provided to demonstrate that they are appropriate.

\*\* “ULN” is the upper limit of the normal range.

#### 9.1.6. Appendix F Severity Grading of Vital Sign Abnormalities

Vital Signs*	Mild (Grade 1)	Moderate (Grade 2)	Severe (Grade 3)	Potentially Life Threatening (Grade 4)
Fever (°C)** (°F)**	38.0 – 38.4 100.4 – 101.1	38.5 – 38.9 101.2 – 102.0	39.0 – 40 102.1 – 104	> 40 > 104

Tachycardia - beats per minute	101 – 115	116 – 130	> 130	ER visit or hospitalization for arrhythmia
Bradycardia - beats per minute***	50 – 54	45 – 49	< 45	ER visit or hospitalization for arrhythmia
Hypertension (systolic) - mm Hg	141 – 150	151 – 155	> 155	ER visit or hospitalization for malignant hypertension
Hypertension (diastolic) - mm Hg	91 – 95	96 – 100	> 100	ER visit or hospitalization for malignant hypertension
Hypotension (systolic) – mm Hg	85 – 89	80 – 84	< 80	ER visit or hospitalization for hypotensive shock
Respiratory Rate – breaths per minute	17 – 20	21 – 25	> 25	Intubation

\* Participant should be at rest for all vital sign measurements.

\*\* Oral temperature; no recent hot or cold beverages or smoking.

\*\*\* When resting heart rate is between 60 – 100 beats per minute. Use clinical judgement when characterizing bradycardia among some healthy participant populations, for example, conditioned athletes.
